**1.23**

Provide the rationale or power analysis to support the number of participants proposed to complete this study.

To be consistent with national reporting guidelines and evidence reviews, the primary cessation outcome will be 7-day point prevalence abstinence measured at 6-months post-baseline. With a baseline sample of 2000 smokers (500 per group) we will have sufficient power for detecting a 5% difference in quit rates between our most intensive condition (Specialized Quitline with Basic Needs Navigator) and least intensive (standard quitline without basic needs navigator) condition for a range of possible quit rates in the sample as a whole. Quit rates were based on the range of 6-month cessation rates from previous Alere clients. We conservatively expect to reach at least 60% of baseline participants at 6-month follow-up, leaving a total sample of at least 1,200 smokers. We would still have sufficient power to detect a 5% difference between groups if OR=1.8 with a total quit rate of 10%, and even greater power for lower quit rates and for intent to treat analyses that include all randomized participants, because non-respondents are assumed to have continued smoking thus overall quit rates would be lower.

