Using a 2x2 randomized factorial design, we will compare the effects of Standard and Specialized Quitlines with and without a Basic Needs navigator on smoking cessation among 2000 low-income smokers. The primary study outcome is self-reported 7-day point prevalence abstinence at 6-month follow up. All contacts with participants will be by telephone. This statewide field trial will recruit smokers who call United Way 2-1-1 Missouri. Smokers interested in quitting and joining our study will complete a phone survey and then be referred to the standard or specialized Missouri Tobacco Quitline, provided by Alere Wellbeing, Inc. Both 2-1-1 Missouri and Alere Wellbeing, Inc./Optum are research partners in this study. Embedding the study in these practice agencies will accelerate the path to application should our findings support it.

**1.4** Specify your research question(s), study aims or hypotheses:

Aim 1: Compare the relative and combined effects of Specialized Quitline services and Basic Needs navigation on use of the Missouri Tobacco Quitline by low-income smokers.

Primary research questions:

- What proportion of smokers in each study group enrolls in and receives Quitline services?
- Of those enrolled, does the number of counseling sessions completed vary by study group?
- Of those enrolled, does use of Quitline services (Print, Text2Stop, WebCoach) vary by study group?

Aim 2: Compare the relative and combined effects of Specialized Quitline services and Basic Needs navigation on quit attempts and abstinence among low-income smokers.

Primary research questions (again, by study group):

- What proportion report 7-day and 30-day point prevalence abstinence at 3 and 6 months?
- What proportion report quitting smoking for at least 24 hours (i.e., make a quit attempt)?
- What proportion report using any pharmacologic cessation aids, like nicotine replacement?

Aim 3: (Dissemination and Implementation Aim) Conduct scalability and economic evaluations to assess the sustainability of the study's referral and intervention approaches.

Primary research question (again, by study group):

A. What are the costs and benefits of each study condition per Quitline referral, per smoker interaction with the Quitline, and per successful quitter from the perspective of Quitline funders and providers?

**1.5** Background and significance and/or Preliminary studies related to this project:

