Strong evidence supports this expectation. In well-designed studies, interventions that address basic needs like housing and food have shown beneficial effects on health behaviors, psychological distress, and mental health outcomes like symptoms of anxiety and depression. Our study will compare the independent and combined effects of two intervention approaches that enhance and extend the traditional behavior-focused approach used by evidence-based tobacco quitlines. The first is an adapted, Specialized Quitline service with heightened attention to contextual conditions in the lives of low-income smokers; the second uses navigators to help low-income smokers address their unmet Basic Needs. Both approaches follow the Institute of Medicine recommendations that social science and behavioral research interventions address individuals' health behaviors as well as the socioenvironmental context in which they live. Specific recommendations included: 1) focusing on social and behavioral determinants of health including economics; 2) using of multiple approaches – one size does not fit all; 3) accounting for the special needs of target groups including social class; and 4) engaging social service and other sectors not traditionally involved in health promotion efforts.

**1.6** Literature cited/references (if attaching a grant enter N/A):

Literature cited in attached grant proposal

**1.7** Describe EACH of your participant populations

Include description of any control group(s)

Specify the Inclusion/Exclusion criteria for EACH group

Inclusion criteria: All participants will be recruited from UnitedWay 211 Missouri and must be 18 years and older, English speaking, not in crisis, smoke cigarettes every day of the week, planning to quit smoking in the next 30 days, comfortable receiving calls from smoking expert and project team, willing to provide phone numbers to be reached, Missouri resident, and will be a resident Missouri in the next 3 months

Exclusion criteria: pregnant or planning to pregnant in the next 3 months, insurance through employer, currently breastfeeding, currently enrolled in smoking quitline. The control group, up to 500 participants, will receive standard quit line services and no basic needs navigator.

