Helping the Poor Quit Smoking: Specialized Quitlines and Meeting Basic Needs

NCT03194958

3/8/17

Provide a summary of the analysis methods you will use, including, if applicable, the data points or outcomes you will analyze.

Aim 1: For each group, descriptive statistics will show the proportion of baseline participants reached by the quitline, number of quitline sessions completed, and additional services (Print, Text2Quit, WebCoach) used. Differences by group will be compared using chi-square tests or logistic regression for categorical variables and by t-tests, linear regression or appropriate non-parametric tests for continuous variables. Secondary analyses will explore any differences by covariates such as gender, age, rural/urban residence, and unmet basic needs. Significant intervention and/or covariate effects will be included in all further analyses.

Aim 2: We will calculate quit rates for each group by dividing the number of participants who meet this criterion by the number of participants randomized to that group. Analysis will follow intent-to-treat (ITT) principles; all participants who completed a baseline assessment and were randomized will be included in analysis. Those lost-to-follow-up, refusing interviews, or otherwise unreachable will be assumed to be smokers. We will use logistic regression to compute odds ratios and 95% confidence intervals for group differences in quit rates, comparing Standard and Specialized Quitlines with and without a Basic Needs Navigator, with the “standard quitline, no navigator” group as the referent.

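### SAP 1.23 claims sufficient power for a 5-point difference with 1,200 respondents, but the contrast it names has 300 per group and about 53–56% power

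*SAP*

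**What the plan says.** The Protocol (1.3) describes the trial this way: "Using a 2x2 randomized factorial design", with 2,000 smokers. SAP 1.23 starts from "With a baseline sample of 2000 smokers (500 per group") and names one contrast for power: Specialized Quitline with Navigator against standard quitline without Navigator, for a 5-point difference in 7-day abstinence at 6 months.

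It then assumes 60% follow-up, "leaving a total sample of at least 1,200 smokers", and claims: "We would still have sufficient power to detect a 5% difference between groups if OR=1.8 with a total quit rate of 10"%. It adds that there is "even greater power for lower quit rates and for intent to treat analyses that include all randomized participants", because counting non-respondents as smokers lowers the overall rate.

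The Aim 2 analysis uses logistic regression, "comparing Standard and Specialized Quitlines with and without a Basic Needs Navigator, with the “standard quitline, no navigator” group as the referent". It divides by the number randomized and sets the missing-data rule: "Those lost-to-follow-up, refusing interviews, or otherwise unreachable will be assumed to be smokers". Protocol 1.7 limits the referent group: "The control group, up to 500 participants, will receive standard quit line services and no basic needs navigator".

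SAP 1.23 gives no alpha, sidedness, numerical power or per-group number after attrition.

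**The concern.** The 1,200 respondents are spread over four groups, but the contrast named in 1.23 uses only two of them. The claim appears to fit all 1,200 split in two. The intent-to-treat sentence raises a second problem. A lower overall rate gives more power only if the absolute difference stays the same, and counting non-respondents as smokers shrinks the absolute difference as well as the rate.

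This paragraph is the documents' only justification of the sample size, and it concerns the primary outcome. If its worked case is not delivered, a null result could be taken as ruling out a 5-point benefit that the trial had roughly even odds of detecting.

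**Working it through.** **Inputs from the documents.** 500 randomized per group, 60% followed up, a 5-point difference, odds ratio 1.8, total quit rate 10% (all SAP 1.23); non-respondents counted as smokers (SAP Aim 2).

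**Assumptions.** Two-sided alpha 0.05, which fits the planned 95% confidence intervals; 80% as the benchmark for sufficient; equal loss across groups; the total rate taken as the midpoint of the two groups compared.

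**Formula** (two proportions, pooled variance under the null, n per group, p̄ the mean of p1 and p2):

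Power = Φ{ [ |p2 − p1| − 1.96·√(2p̄(1−p̄)/n) ] / √( [p1(1−p1) + p2(1−p2)]/n ) }

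**Step 1: the effect.** Five points around 10% is 7.5% against 12.5%, an odds ratio of (0.125 × 0.925)/(0.075 × 0.875) = 1.76. An odds ratio of exactly 1.8 at a 10% mean is 7.41% against 12.59%. The SAP's three figures agree with each other.

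**Step 2: where the claim reproduces.** The SAP gives no percentage to match. With all 1,200 split 600 against 600, power is 82% (7.5% v 12.5%) or 85% (odds ratio 1.8).

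**Step 3: the named contrast.** Respondents per group: 1,200/4 = 300. For 7.5% v 12.5%, the null standard error is √(2 × 0.1 × 0.9/300) = 0.02449, and × 1.96 gives 0.04801. The alternative standard error is 0.02441. So (0.05 − 0.04801)/0.02441 = 0.08, and power is 53%.

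| n per group | 7.5% v 12.5% | OR 1.8 |
|---|---|---|
| 300 | 53% | 56% |
| 500 | 75% | 78% |
| 600 | 82% | 85% |

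Exact enumeration of the chi-square test gives 54% and 57% at n = 300. One-sided 0.05 gives 65–68% at 300 and 84–86% at 500. If 10% is read as the control rate, two-sided power at 300 is 46% (10% v 15%) or 67% (odds ratio 1.8), and at most 78% one-sided. No variant at 300 per group reaches 80%.

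**Step 4: what 80% needs.** At a 10% total, 564 respondents per group for 7.5% v 12.5% and 526 for odds ratio 1.8. At 60% follow-up that is 564/0.6 = 940 or 526/0.6 = 877 randomized per group. The difference detectable with 80% power at a 10% total is 6.8 points at n = 300 and 5.3 points at n = 500. A 5-point gap reaches 80% at totals of about 8.7% or lower with 500 per group, and about 5.1% or lower with 300.

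**Step 5: lower quit rates, n = 300.**

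| Total | 5 points held | OR 1.8 held |
|---|---|---|
| 10% | 53% | 56% |
| 8% | 62% | 48% |
| 6% | 73% | 39% |

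Power rises only if the absolute gap is held. With the odds ratio held, it falls.

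**Step 6: intent-to-treat, 500 per group, 60% follow-up.** A 10% respondent rate becomes 0.6 × 10% = 6%.

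| Held constant | Rates | Power |
|---|---|---|
| 5 points on the intent-to-treat scale | 3.5% v 8.5% (OR 2.56) | 92% |
| OR 1.8 | 4.38% v 7.62% | 58% |
| Respondent effect carried through, 5 points | 0.6 × 7.5% = 4.5% v 0.6 × 12.5% = 7.5% | 51% |
| Respondent effect carried through, OR 1.8 | 4.45% v 7.55% | 54% |

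The first row requires 5/0.6 = 8.3 points among respondents (5.83% v 14.17%, odds ratio about 2.7). With the respondent effect carried through, power is 65–68% at 80% follow-up and 75–78% at 100%. At a 6% total and 500 per group, the detectable difference is 4.2 points, or 4.2/0.6 = 7.0 among respondents.

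**The case against.** - **300 per group is not the primary analysis.** Correct. The primary intent-to-treat comparison keeps 500 per group; 300 is the complete-case sensitivity set. But the SAP offers the 1,200-respondent case itself and says power still suffices there, and 500 per group at a 10% total gives 75–78%.
- **A factorial margin may have been meant.** The sentence says only that the difference is between groups, and 600 against 600 is natural in a 2x2 design. This may well explain the claim. However, 1.23 defines no margin, and Aim 2 compares groups with one referent cell. If a margin was intended, the text still has to say so.
- **The intent-to-treat clause is true if its object is the 5-point difference.** This is the most natural grammatical reading, and it gives 92%. But the same passage gives an odds ratio of 1.8, which matches 5 points only near a 10% total. The missing-data rule it relies on also shrinks the stated respondent effect to about 3 points.
- **The primary analysis may sit in the favourable region.** Protocol 1.13 expects fewer than 168 abstinent respondents; 168/2,000 = 8.4%, where a 5-point gap at 500 per group has 81% power. This has some force. But that count excludes users of nicotine replacement, so total abstinence could be higher, and 5 points on this scale still means 8.3 among respondents at 60% follow-up.
- **The 80% benchmark is imported.** True. It matters at 500 per group, where one-sided testing passes it, but not at 300.

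**Conclusion.** The concern holds. For the only contrast SAP 1.23 names, power with 1,200 respondents at a 10% total is about 53–56%, against the 82–85% that would justify the claim. This rests on two-sided alpha 0.05 and equal follow-up across groups; one-sided testing raises it only to 65–68%.

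The opening statement, with 500 per group over a range of quit rates, is sound for a 5-point gap at totals of about 8.7% or lower. The intent-to-treat assurance is true on one reading only: power runs from 51% to 92% depending on a choice the text leaves unstated. A reader cannot tell from 1.23 what difference the trial can detect. The wording must be corrected.

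**What to change.** In SAP 1.23:

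1. State alpha, sidedness, target power, the contrast and the number per group.
2. Restate power for the extreme-group contrast at a 10% total as about 53–56% with 300 respondents per group (the complete-case set) and 75–78% with 500. Add that 500 per group reaches 80% for a 5-point gap at totals of about 8.7% or lower.
3. Replace the unqualified intent-to-treat clause with power on that scale, naming the effect held constant and the follow-up rate: 92%, 58% or 51–54%, as in step 6.
4. Give the detectable differences: 6.8 points (300 per group) and 5.3 points (500 per group) at a 10% total, and 4.2 points (500 per group) at a 6% intent-to-treat total.
5. If a factor-margin comparison was intended, say so and quote its power: 82–85% for 600 against 600 respondents, or 81–83% for 1,000 against 1,000 randomized at the diluted rates. Both assume the whole gap lies on one factor.

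The cost is SAP wording and a less favourable stated power at a 10% total. Enrolment, data collection and analysis are unchanged.
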